## 6.0 STATISTICAL CONSIDERATIONS

### 6.1 Statistical analysis

All subjects who received one dose of study drug will be included in the safety analysis. Each primary and secondary efficacy outcome measure will be analyzed for the intent-to-treat (ITT) and evaluable population. The intent-to-treat principle is that participants will be analyzed in the groups to which they were randomized, regardless of whether they received the randomized study medication.

Data will be summarized as frequency with percentage for categorical clinical variables, and as mean  $\pm$  standard deviation or median with interquartile range for continuous variables. The difference between dupilumab and placebo arms will be tested with Chi-square for categorical measures (e.g., the primary endpoint) and two-sample t-test or Wilcoxon rank sum test for continuous measures (e.g., biomarkers). Due to the relatively small sample size in the study, the adjusted treatment effect of dupilumab will be estimated exploratively in generalized linear regression for the primary and secondary outcomes to account for the potential impact of patient characteristics (e.g., age, sex, race and co-morbidities) and baseline biomarker measures. Data transformation will be considered for the outcomes with skewed distribution. The difference in the biomarker measures at the follow-up visit and their changes from baseline between dupilumab and placebo groups will also be assessed. Since this is intended to be an early stage, proof of concept study for which the primary goal is to inform future trials rather than to perform formal hypothesis testing, no multiplicity adjustment is planned.

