### 6.2 Sample Size justification

Under the protocol HSR 210184, we conducted a randomized double-blind placebo-controlled trial assessing the safety and efficacy of dupilumab for treating hospitalized patients with acute moderate to severe COVID-19, which was designed as an early stage (Phase IIa) and proof of concept study. A total of 40 patients were enrolled from June 23, 2021 through November 180 11, 2021 in the Phase IIa study, and 7 of them died by Day 60. The sample size of 40 in the original Phase II study were determined largely based on the feasibility with a primary goal to collection reliable data and obtain sufficient evidence for future trials. The current proposed study is an extension of the original Phase IIa study under the HSR 210184, to assess the post recovery of remaining 33 patients from COVID-19 with respect to pulmonary function testing (PFT), pulmonary imaging, immune biomarkers and symptoms at one-year follow-up. All data will be collected at a single visit, 1 year (i.e.,  $365 \pm 90$  days) after initial enrollment in the remaining 33 parents from the study HSR 210184. Formal sample size estimation and power analysis is not performed due to the pilot nature of this proposed follow-up study.

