1.0 Introduction

1.1 Study objectives: The primary objective is to determine the efficacy of dupilumab use plus standard of care management in patients hospitalized with moderate to severe COVID-19 infection compared to placebo plus standard of care management assessed by the proportion of patients alive and free of invasive mechanical ventilation at 28 days. The secondary objectives are to: (1) evaluate the safety of Dupilumab use in terms of eosinophilia in patients hospitalized with moderate to severe COVID-19 infection, (2) compare clinical outcomes on Dupilumab versus placebo across a range of secondary clinical safety and efficacy domains, and (3) evaluate the immunologic and biologic end points of inhibition of type 2 inflammation.

1.2 Study design: This is a randomized, double-blind, placebo-controlled, superiority phase IIa trial to assess the safety and efficacy of dupilumab use in hospitalized patients with moderate to severe COVID-19 infection. A total of 40 eligible subject will be enrolled and randomized in a 1:1 ratio to receive either dupilumab or placebo, stratifying on the disease severity measured by the required oxygen $\leq 15\text{L}$ or $> 15\text{L}$ by nasal cannula. Both arms will receive standard of care management per current National Institutes of Health (NIH) COVID-19 treatment guidelines (<https://covid19treatmentguidelines.nih.gov/>) in addition to their randomized treatments. Patients will be followed prospectively for up to 60 days after enrollment.

1.3 Database Sources: Completed forms and electronic data will be entered into the data management system in the REDCap platform. Only authorized individuals shall have access to electronic CRFs.

1.4 Randomization:

In this randomized, double-blind, placebo-controlled Phase IIa trial, a total of 40 eligible subjects will be enrolled and randomized in a 1:1 ratio to receive either dupilumab or placebo, stratifying on the disease severity, which is measured by the required oxygen $\leq 15\text{L}$ or $> 15\text{L}$ by nasal cannula. Both arms will receive standard of care management per current National Institutes of Health (NIH) COVID-19 treatment guidelines (<https://covid19treatmentguidelines.nih.gov/>) in addition to their randomized treatments.

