3.4 Software: All analyses will be performed utilizing SAS® version 9.4. All statistical tests will be conducted at the 5% Type I error rate (two-sided). When multiple tests are conducted, the chance of finding a significant difference in one of the tests, when in fact no difference exists, is greater than the stated Type I error rate. The investigators are aware of the multiple testing issues and will interpret results with caution and use confidence intervals where possible.

4.0 Analysis of demographic and baseline data:

The demographic variables for this study include age, gender, race, ethnicity, and BMI, etc. The baseline clinical characteristics include disease severity, symptoms, comorbid conditions, days

from COVID-19 symptom onset, and baseline blood lab results, etc.

Descriptive statistics for baseline and demographic variables will be presented for patients randomized to each of the treatment arms and overall. Descriptive statistics will include N, mean, standard deviation, median, 25th and 75th percentiles, minimum and maximum for continuous variables and proportions and percentages for categorical variables. In general, randomization is expected to produce balance at baseline between the two arms of the trial, formal statistical comparisons of treatment groups with respect to baseline characteristics will not be necessary. However, since this is a relatively small study, the differences in baseline characteristics between the treatment arms will be evaluated exploratorily for better understanding the study population. The updated CONSORT statement no longer recommends formal testing of statistical significance of differences between baseline characteristics.

5.0 Efficacy analyses:

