5.3 Secondary outcomes

5.3.1 Eosinophilia as the safety outcome: Eosinophilia is a binary indicator for a patient

to have an absolute eosinophil count $> 0.6 \text{ k}/\mu\text{l}$ at ≥ 1 measurement based on the blood counts with differentials and complete metabolic panels on Day 0, 2, 5, 7, 14, 28 and 60 (Data on Day 7, 28 and 60 would be optional). The outcome will be summarized as the proportion of patients with eosinophilia and the difference in the proportions between the two study arms will be evaluated with Chi-square test. The odds ratio of having eosinophilia for Dupilumab vs. placebo and its 95% CI will also be estimated in logistic regression, with adjustment for other covariates.

5.3.2 Other secondary safety and efficacy outcomes:

- Cumulative incidence rate of adverse events (injection site reactions, eye/eyelid inflammation, conjunctivitis, oropharyngeal pain, insomnia, tooth ache, gastritis, arthralgia, bacterial pneumonia, herpes viral infection, hypereosinophilic syndrome, hypersensitivity reaction, other grade 3 or 4 adverse events, serious adverse events or death) is defined as number of adverse events divided by the total number of individuals in the population at risk for the time interval. The rate ratio of adverse events for Dupilumab vs. placebo and its 95% CI will be analyzed in Poisson regression, in which the follow-up time interval will be considered as the offset. Adjusted analysis for other covariates will be performed, as necessary. Mortality at 60 days will be analyzed as the time to event response. Survival probabilities will be estimated by the Kaplan-Meier method, and the difference in the mortality risk between the two treatment groups will be evaluated by the log-rank test and further in Cox regression, adjusting for the baseline covariates. For the analysis of mortality over the first year, additional adjustment for dynamic mechanical ventilation effect will be considered by including being on ventilation as a time-vary covariate in the Cox regression.
- Plasma total Immunoglobulin E (IgE) levels on Day 0 and 14 will be considered as continuous responses, and difference between treatment arms will be evaluated by t-test or Wilcoxon test initially, and adjusted difference and its 95% CI will be estimated from linear regression. Further, changes of IgE from Day 0 to Day 14 will also be explored and the difference between the two study arms will be analyzed similarly.

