This trial is intended to be an early stage and proof of concept study with the primary goal to collect reliable data and obtain sufficient evidence for future trials. Thus, the emphasis of the study is an exploratory estimation of effect size and incidence of adverse events in terms of eosinophilia; it is not considered as a pivotal trial for efficacy at this time. Therefore, a larger significance level (one-sided alpha=0.1), and the sample size is pre-selected based on the feasibility. Given the current decline trend in the incidence of COVID-19 positive cases, we anticipate to enroll 40 patients realistically into this randomized clinical trial, which shall be sufficient for us to collect reliable and interpretable data for proof of concept to inform future trials. The COVID-19 hospitalization data from our University of Virginia Health System between March 2020 and April 6, 2021 showed that 79.5% of COVID-19 inpatients were alive and free of mechanical ventilation at 28 days under the usual care. With 40 patients that are deemed to be feasible, we would expect Dupilumab to improve a margin of 17.7% in the proportion of patients alive and free of mechanical ventilation at 28 days. That is, it is anticipated that 97.2% of patients being alive and free of ventilation at 28 days in the Dupilumab arm. The power analysis is conducted using the one-sided Score test (Farrington & Manning) with 75% power and 10% type I error.

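### Day 14 IgE and the 1-year biomarkers: the lead comparison should adjust the follow-up value for the Day 0 value, which the plan does not name for IgE and makes only exploratory at 1 year

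*SAP*

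**What the plan says.** **Day 14 IgE (SAP 5.3.2).** "Plasma total Immunoglobulin E (IgE) levels on Day 0 and 14 will be considered as continuous responses". The arms are compared first by t-test or Wilcoxon test. An adjusted difference with a 95% confidence interval then comes from linear regression, with no covariates listed in that paragraph. The text adds that "changes of IgE from Day 0 to Day 14 will also be explored", by similar methods. SAP 5.1 gives age, sex, race and co-morbidities as examples of adjustment variables; the Day 0 biomarker value is not among them.

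**CRP and ferritin (SAP 5.3.2).** These go into a mixed model, but revert to the IgE method if Day 7 is not available for all patients. Day 7 is optional after discharge.

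**1-year biomarkers (Protocol 6.1).** The stated test is an unadjusted t-test or Wilcoxon test. Follow-up values are compared and "their changes from baseline between dupilumab and placebo groups will also be assessed". An exploratory generalized linear regression accounts for patient characteristics and for baseline biomarker measures.

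**Baseline comparisons.** SAP 4.0 says formal testing of baseline differences is unnecessary in a randomised trial, though it allows an exploratory look. SAP 5.3.2, on CRP and ferritin, says no treatment effect on the intercept is expected.

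**The concern.** In a randomised comparison the Day 0 value cannot be affected by treatment, so its use is as a covariate. The plan names it as a response for IgE and does not name it as a covariate for Day 14. At 1 year it enters only an exploratory model alongside several other covariates, which is a heavy load for at most 33 patients. In neither place does the plan say which of the follow-up comparison, the change score and the adjusted estimate leads.

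What is at stake is precision. SAP 7.0 puts the emphasis on exploratory estimation of effect size, so in a study this small the choice of estimator affects what can be learned. The change score is the weakest choice when baseline and follow-up are loosely related. With no lead named, a reader also cannot tell in advance which result for each marker is to be believed.

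**Working it through.** **The plan's own figure.** The only design figure is 75% power for the Day 28 primary endpoint (79.5% against 97.2%, one-sided 10%, 20 per arm). Exact enumeration of the one-sided score test gives 75.1%, so it reproduces. It says nothing about biomarkers, for which the documents state no power, SD, effect size or correlation.

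**Inputs.**
- Parent trial (SAP 1.2): "A total of 40 eligible subject will be enrolled and randomized in a 1:1 ratio". N is at most 40 for Day 14 IgE.
- Extension (Protocol 6.2): "to assess the post recovery of remaining 33 patients from COVID-19". N is at most 33 at 1 year.
- Day 0 IgE, CRP, ferritin and cytokines are scheduled in SAP 2.2.2.
- Assumed: correlation r between Day 0 and follow-up, and equal variances at the two times (after transformation if needed).

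**Formulas.** Variance of the arm difference, relative to the unadjusted follow-up comparison (= 1):
- change score: 2(1 − r)
- follow-up adjusted for baseline: (1 − r²) × (N − 3)/(N − 4); the last factor is the cost of estimating the slope
- adjusted also for a stratum that turns out uninformative: (1 − r²) × (N − 3)/(N − 5)

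At N = 33 the two factors are 30/29 = 1.034 and 30/28 = 1.071. At N = 40 the first is 37/36 = 1.028.

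| r | Change score | Baseline-adjusted, N = 33 | Plus uninformative stratum, N = 33 | Baseline-adjusted, N = 40 |
|---|---|---|---|---|
| 0 | 2.0 | 1.034 | 1.071 | 1.028 |
| 0.3 | 1.4 | 0.91 × 1.034 = 0.941 | 0.91 × 1.071 = 0.975 | 0.935 |
| 0.5 | 1.0 | 0.75 × 1.034 = 0.776 | 0.75 × 1.071 = 0.804 | 0.771 |
| 0.7 | 0.6 | 0.51 × 1.034 = 0.528 | 0.51 × 1.071 = 0.546 | 0.524 |

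A simulation with 40,000 runs per setting agrees: at N = 33, baseline adjustment gave 1.033, 0.775 and 0.531 at r = 0, 0.5 and 0.7.

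**Break-even points.**
- Against the follow-up test at N = 33: (1 − r²) × 30/29 = 1 gives r² = 1/30, r = 0.18. At N = 40, r² = 1/37, r = 0.16. With an uninformative stratum at N = 33, r² = 2/30, r = 0.26. Below these values adjustment loses slightly.
- Against the change score at N = 33: adjustment is better while (1 + r) × 30/29 < 2, that is, r below about 0.93.

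**What this means for a test.** For an assumed 0.8 SD effect, two-sided 5%, N = 33 in near-equal arms and baseline as the only covariate:
- r = 0.2: power 60.5% (follow-up), 42.1% (change), 60.7% (adjusted)
- r = 0.5: 60.5%, 60.5%, 71.4%
- r = 0.7: 60.5%, 82.0%, 86.5%

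At r = 0.5 the adjusted confidence interval is about 12% narrower than either alternative.

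**The case against.** The strongest reply is that much of this is already planned. SAP 5.3.2 promises an adjusted IgE difference with a confidence interval and uses the unadjusted test only as a first step. The covariates in SAP 5.1 are examples, so Day 0 IgE is not excluded, and SAP 4.0 counts baseline blood results among baseline characteristics. Protocol 6.1 names baseline biomarker measures outright. A reader might infer that the biomarkers are compared only by unadjusted tests; these passages rule that out. What stands is that the Day 0 value is not named for IgE and that baseline adjustment is not the lead analysis in either place.

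A reader might also infer that every biomarker is affected. The parent-trial cytokines go into longitudinal mixed models that include Day 0, and this point does not reach them.

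It is also tempting to say that adjustment is free, or that it makes 40 patients worth about 53. The second figure is 40/0.75: it assumes r = 0.5, leaves out the slope cost and uses an N not available at 1 year. Nor do the documents support calling a low 1-year correlation likely. If r is low, adjustment gains little over the follow-up test, though that is where the change score does worst.

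Finally, the formulas assume equal variances and a t-type comparison. Variances in acute illness and after recovery may differ, and no comparison with the Wilcoxon test was made. Both limits stand.

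**Conclusion.** The point holds in a limited form. For Day 14 IgE, and for CRP and ferritin under the fallback, the plan leads with unadjusted tests, does not name Day 0 as a covariate and lists Day 0 IgE as a response, which sits badly with SAP 4.0. At 1 year, baseline adjustment is planned but is exploratory and mixed with other covariates.

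The size depends on an r that the documents do not give. At 33 patients the worst case for baseline adjustment is about 3% more variance than the follow-up test (about 7% with an uninformative stratum), and at r = 0.5 it saves about 22%. The change score ranges from double the variance at r = 0 to a 40% saving at r = 0.7, where adjustment saves 47%. With r unknown, baseline adjustment is the robust choice.

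These are secondary markers in a proof-of-concept study. No bias is shown and no primary conclusion changes. Nor does adjustment remove the selection that comes from studying only survivors who attend at 1 year.

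**What to change.** State in SAP 5.3.2 and Protocol 6.1 that the lead analysis of Day 14 IgE, of CRP and ferritin under the fallback, and of each 1-year biomarker is a regression of the follow-up value (transformed if skewed, with Day 0 on the same scale) on arm, the Day 0 value and the oxygen stratum used at randomisation. Keep the t-test or Wilcoxon test as supportive and change scores as descriptive. Do not analyse Day 0 as an outcome. Leave the parent-trial cytokine mixed models as they are. State how patients without a Day 0 value are handled.

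Protocol 1.0 and 3.2 already describe parent-trial results. If the Day 14 IgE data have been analysed, label the adjusted result post hoc; the 1-year analysis is where fixing the lead in advance matters most.

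The cost is a few sentences, two degrees of freedom, the small variance penalty shown above if the covariates prove uninformative, and the handling of missing Day 0 values. No new measurements are needed.

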- Plasma inflammatory markers (C-reactive protein and ferritin) on Day 0, 7 and 14 (Day 7 would be optional if patient discharged) will be analyzed as longitudinal responses in the linear mixed effects model with Dupilumab treatment as a fixed effect. Since this is a randomized study, significant effect of treatment on intercept is not expected. Thus, the longitudinal analysis will focus on the slope difference between the treatment arms via interaction of treatment and time in the model. Since there are only 3 measures for each subject, only random slopes will be specified as *a priori*. Model fitting indices will be examined carefully to ensure the validity of estimated parameters. If Day 7 data won't be available for all patients, these biomarkers between Day 0 to Day 14 will be analyzed as the IgE above.
- Plasma cytokine levels including TARC (CCL17), YKL40, eotaxin 3 (CCL26), IL-13, IL-4, Arg 1, Hyaluronan, soluble ST2 on Day 0, 2, 5, 7, 14, and 28 (Day 7 and 28 optional if patient discharged) will be analyzed as longitudinal responses

in the linear mixed effects model with Dupilumab treatment as a fixed effect, and with appropriate transformation of biomarkers if necessary. The trajectories of these biomarkers will be carefully evaluated, and the slope difference between the treatment arms will be evaluated by the interaction of treatment and time.

Additional curvature in trajectories will also be explored and captured whenever possible in the linear mixed effects model.

- Change in $\text{PaO}_2/\text{SaO}_2$ to FiO_2 ratio on Day 0, 2, 5, 7 (if patient remains inpatient throughout) will be analyzed as longitudinal responses in the linear mixed effects model, similar methods to that for inflammatory biomarkers and cytokine biomarkers as described above.
- All-cause mortality at 28 days will be analyzed as the binary response, using the same methods as that for the primary efficacy outcome and eosinophilia.
- Hospital length of stay (LOS) and ICU LOS between treatment arms will be analyzed as continuous measures using t-test or Wilcoxon test initially, and adjusted difference and its 95% CI will be estimated from linear regression. Since the distributions of hospital LOS and ICU LOS are often skewed, the log-transformed LOS data will be considered in the analyses.
- The response of being alive and free respiratory failure at 28 days is a binary response and will be analyzed using the same methods as that for the primary efficacy outcome.

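### A common Day 0 mean would sharpen the CRP/ferritin and cytokine slope comparisons, but only if the random-effects specification changes with it

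*SAP*

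**What the plan says.** SAP 5.3.2 covers three groups of repeated measurements.

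- **CRP and ferritin**, measured on "Day 0, 7 and 14 (Day 7 would be optional if patient discharged"), are "analyzed as longitudinal responses in the linear mixed effects model with Dupilumab treatment as a fixed effect". The text expects no arm difference at the start ("Since this is a randomized study, significant effect of treatment on intercept is not expected") and bases the comparison on "the slope difference between the treatment arms via interaction of treatment and time in the model". On the random effects it says: "Since there are only 3 measures for each subject, only random slopes will be specified as" the a priori choice. If Day 7 is not available for everyone, these markers move to the two-time-point approach used for IgE.
- **Plasma cytokines**, on Days 0, 2, 5, 7, 14 and 28, are analysed "in the linear mixed effects model with Dupilumab treatment as a fixed effect, and with appropriate transformation of biomarkers if necessary", and "the slope difference between the treatment arms will be evaluated by the interaction of treatment and time". Neither the expectation about the intercept nor any random-effects structure is stated for them.
- **Change in the PaO2/SaO2 to FiO2 ratio** is to use "similar methods to that for inflammatory biomarkers and cytokine biomarkers as described above", for patients who remain inpatient.

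No model equation is written, and nothing sets the Day 0 arm difference to zero.

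**The concern.** An effect of treatment on the intercept exists only if a treatment main effect is in the model. So the SAP appears to estimate a Day 0 arm difference that randomisation makes zero in expectation, as the SAP itself says. The estimated Day 0 difference and the estimated slope difference are negatively correlated. A chance imbalance at Day 0 therefore carries over into the slope difference, which is the treatment comparison named for the longitudinal analysis.

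At stake is precision. SAP section 7.0 fixes the sample at 40 on feasibility grounds and puts the emphasis on estimating effect size for later trials. Precision that costs no patients is worth having there.

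**Working it through.** **The plan's own figure.** The only computed design figure is 75% power for the binary primary endpoint (SAP 7.0). Exact enumeration of the one-sided score test at 20 per arm, 79.5% versus 97.2%, alpha 0.10, gives 75.1%, so it reproduces. It says nothing about biomarker slopes, for which the documents give no power, SD or correlation.

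**Inputs.** From the SAP: 40 patients randomised 1:1 (20 per arm) and the visit days. Assumed: Day 0 SD of 1, complete data, linear time, and a share ρ of Day 0 variance lying between patients (the within-patient correlation), from 0.3 to 0.9.

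**Step 1: gain with a random intercept.** Fixing the Day 0 difference at zero cuts the variance of the slope difference by the squared correlation between the two estimates. With m visits, mean time t̄ and sum of squares Sxx:

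cut = (1−ρ)B / [ρ + (1−ρ)A], where B = t̄²/Sxx and A = 1/m + B.

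- Days 0/7/14, scaled to 0, 0.5, 1: t̄ = 0.5, Sxx = 0.5, B = 0.5, A = 0.8333.
- Days 0/2/5/7/14/28: t̄ = 56/6 = 9.333, Sxx = 1058 − 56²/6 = 535.33, B = 87.11/535.33 = 0.1627, A = 0.3294.

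| ρ | Days 0/7/14 | Cytokine days |
|---|---|---|
| 0.3 | 0.350/0.883 = 39.6% | 0.1139/0.5306 = 21.5% |
| 0.5 | 0.250/0.917 = 27.3% | 0.0814/0.6647 = 12.2% |
| 0.7 | 0.150/0.950 = 15.8% | 0.0488/0.7988 = 6.1% |
| 0.9 | 0.050/0.983 = 5.1% | 0.0163/0.9329 = 1.7% |

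**Step 2: add a random slope.** Take a slope SD of 0.5 over 14 days, independent of the intercept. For Days 0/7/14 the free-model variance is (2/20) × [(1−ρ)/0.5 + 0.25]. At ρ = 0.5 this is 0.1 × 1.25 = 0.125, SE 0.354. The cut becomes 0.25/(0.917 × 1.25) = 21.8%, so the constrained SE is 0.354 × √0.782 = 0.313. At ρ = 0.3 and 0.7 the SEs are 0.406 to 0.331 and 0.292 to 0.275. An effect with 80% power under the free model (two-sided 5%) would have about 93%, 89% and 84% power at ρ = 0.3, 0.5 and 0.7. The SE reductions are 18.5%, 11.6% and 5.7% for three visits, and 5.6%, 2.6% and 0.9% for the cytokine days.

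**Step 3: drop the main effect but keep random slopes only.** With no random intercept, the constrained estimate is a line through the origin fitted to the arm difference. With Σt = 1.5 and Σt² = 1.25, its true variance is 0.1 × [1.44ρ + 0.8(1−ρ) + 0.25]. The model itself, treating all Day 0 variance as residual, reports 0.1 × (0.8 + 0.25) = 0.105, SE 0.324.

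| ρ | True SE, free | True SE, constrained, slopes only | SE it reports | Constrained, with random intercept |
|---|---|---|---|---|
| 0.3 | 0.406 | 0.352 | 0.324 | 0.331 |
| 0.5 | 0.354 | 0.370 | 0.324 | 0.313 |
| 0.7 | 0.292 | 0.387 | 0.324 | 0.275 |

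The two true SEs cross where 2(1−ρ) = 0.8 + 0.64ρ, at ρ of about 0.45. If slopes-only were also used for the cytokines, the true SE at ρ = 0.5 would go from 0.208 to 0.248 (slope SD 0.5 over 14 days).

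**Step 4: sensitivity to intercept-slope correlation.** If patients who start high fall faster (correlation −0.5), the gain with a proper covariance is larger: up to 27.9% in SE for three visits and 19.5% for the cytokine days. The slopes-only variance in Step 3 then changes by 0.1 × 2.4 × (−0.25√ρ). The constrained SE becomes 0.308 against 0.354 at ρ = 0.5, and 0.316 against 0.292 at ρ = 0.7. The harm then starts at a higher ρ, but it is not removed.

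**The case against.** The strongest objection is that simply removing the treatment term can backfire. Under the slopes-only wording for CRP/ferritin, that term is what absorbs chance Day 0 imbalance. Step 3 shows this is right. It stands, and it decides the form of the fix.

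A reader might also infer more than the documents support:

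- **That the plan is in error or biased.** It is not. Treatment, time and their interaction form a standard, unbiased model, and even the free Day 0 term is inferred from wording.
- **That the slope is the only treatment test for these markers.** SAP 5.1 names a two-sample t-test or Wilcoxon test as the initial test for continuous measures, including biomarkers. The IgE-type fallback may also replace the mixed model for CRP/ferritin, since Day 7 is optional after discharge. The three-visit figures may then never apply.
- **That the oxygenation ratio should be treated the same way.** That outcome is described as a change and limited to patients who stay in hospital. Staying in hospital is determined after randomisation, so equal Day 0 means are not assured. If the outcome is change from Day 0, there is no Day 0 difference to constrain.
- **That the gain is known to be large.** No correlations are given, and at high correlation it nearly vanishes.

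Timing also counts. The protocol summary says parent-trial enrolment closed in November 2021 and that 60-day results are known. The documents do not say whether the biomarker models have been run.

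**Conclusion.** The point holds as an optional efficiency gain for the cytokines, and for CRP/ferritin when the mixed model is used. With a random intercept, the variance of the slope difference falls by about 16-40% (Days 0/7/14) and 6-22% (cytokine days) at ρ from 0.7 down to 0.3. The cut is smaller with independent random slopes, and about 0-5% at ρ = 0.9. These sizes rest on 20 per arm, complete data, linear time and assumed correlations.

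The direction is firm if the covariance is right and the Day 0 sample is pre-dose, which the documents do not state outright. With random slopes only and independent intercepts and slopes, removing the main effect raises the true SE at ρ of 0.5 and above for three visits, while the reported SE is too small.

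The 1-year follow-up analysis in protocol 6.1 uses two-sample tests and exploratory regression that can include baseline biomarkers, so it is not affected.

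**What to change.** In SAP 5.3.2, for the cytokines, and for CRP/ferritin whenever the mixed model is used:

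1. Fit a constrained longitudinal model: one Day 0 mean common to both arms, time, and treatment-by-time.
2. In the same edit, replace the slopes-only rule for CRP/ferritin with a random intercept (plus a random slope if it can be fitted) or an unstructured covariance. State the structure for the cytokines, where none is given. Do not make change 1 without change 2.
3. Limit this to markers whose Day 0 sample is taken before the first dose in all randomised patients, and say so. Leave out the PaO2/SaO2 to FiO2 change outcome.
4. Write out the model equation, so that the treatment of Day 0 need not be inferred.

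The cost is a few sentences and slightly more modelling work, with no new data. The price is reliance on a pre-dose Day 0 sample. An unstructured covariance over six cytokine visits has 6 × 7/2 = 21 parameters, which is heavy for 40 patients, so name the random-intercept form as the fallback. If the biomarker models have already been run, report the constrained model as a dated, supplementary analysis.
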